14.2.4 Pregnancy

Pregnancy occurring in a subject is NOT considered an AE. However, the investigator must collect pregnancy information for subject and/or subject's partner if the fetus was exposed to the study drug.

14.3 Reporting of Adverse Events/Serious or Unexpected Adverse Reactions or Adverse Events

14.3.1 Site Reporting to Sponsor

Investigators must report all serious AEs to the sponsor (and applicable IRB) whether or not the events are study drug-related or expected. In the event of the death of a subject,

Terlipressin
Protocol MNK19013058
Incorporating Amendments 1, 2 and 3

the investigator-reported immediate cause of death will be collected and recorded on the appropriate eCRF page.

All serious AEs must be reported on a serious AE form and faxed to Mallinckrodt within **24 hours** of an investigator becoming aware of the event:

Drug and Device Safety and Pharmacovigilance

Fax:

Email: [contact]

If no fax confirmation received within 1 business day by the reporter, notify Global Pharmacovigilance via phone or email: [contact] or [contact].

The initial serious AE form does not need to be signed by the investigator; however, a signed serious AE form is required within 72 hours of faxing to Mallinckrodt. The initial fax by the investigator will include a detailed description of the event including start and stop dates, causality assessment by the investigator, and supported as needed with written copies of medical records, autopsy reports, and other appropriate documents. Follow-up information (including information requested by the sponsor) should be reported by fax within 24 hours of availability. The investigator is expected to make every effort to collect follow up information for each SAE in a timely fashion after the initial reporting of the SAE.

If there are any specific questions regarding an AE being classified as serious, the investigator should contact the Medical Hotline for this study. The hotline number will be provided in the Site/Investigator Study Manual. Refer to Section 10.9.

If there are any specific questions regarding the completion of the serious AE form, please contact the site monitor.

14.3.1.1 Overdose

In the event of an overdose, the investigator will be required to report this event to the sponsor using a serious AE form, following the SAE reporting timeline.

14.3.1.2 Pregnancy

In the event of pregnancy, the investigator will be required to report this event to the sponsor using the Pregnancy Surveillance Form. Pregnancy should be followed up by the investigator until delivery and the neonatal outcome must be reported.

14.3.2 Site Reporting to Institutional Review Board/Independent Ethics Committee

The investigator must notify the local IRB which approved the trial of the event in accordance with applicable guidelines.

14.3.3 Sponsor Reporting to Regulatory Authorities and Investigators

All reportable AEs, including narrative safety reports of overall findings or data from aggregate analyses, will be reported to the applicable regulatory authorities by the sponsor or designee in accordance to the local regulations as described in the safety review plan for this study. The reporting of serious AEs will be conducted in accordance with ICH E2A (Clinical Safety Data Management: Definitions and Standards for expedited reporting) and regulatory guidelines.

In addition, study endpoints described in Section 6.1 of the protocol that are serious adverse events will only be reported in the final clinical study report unless the event was unusual, unexpected, and there is evidence suggesting a causal relationship between the study drug and the event (eg, death from anaphylaxis).

The sponsor will notify all participating investigators of safety reports, in a blinded fashion, of potential serious risks as described in the safety review plan for this study.

15 Statistical Plan

This is a randomized, double-blind, placebo-controlled, multicenter study of intravenous terlipressin in subjects with HRS Type 1. All subjects who consent to study participation must undergo an in-hospital screening/qualification period of no less than 48 hours prior to enrollment in order to establish the diagnosis of HRS Type 1. Written informed consent will be obtained by the investigator, sub-investigator or qualified designee from the subject or legally-authorized representative prior to the subject qualification form being completed. Qualified subjects are then randomized in a 2:1 ratio to receive either terlipressin or placebo, stratified by qualifying SCr (less than 3.4 mg/dL or at least 3.4 mg/dL) and LVP (at least one single event of at least 4 L or less than 4 L within 14 days prior to randomization). A total of 300 subjects are planned to be enrolled at approximately 70 sites in the United States and Canada.

Randomization will be done centrally using an IXRS stratified by qualifying SCr (less than 3.4 mg/dL or at least 3.4 mg/dL) and pre-enrollment LVP (at least one single event of at least 4 L or less than 4 L within 3 to 14 days prior to randomization). Note, subjects with a LVP of at least 4 L are excluded if it occurs within 2 days prior to randomization (refer to

Terlipressin
Protocol MNK19013058
Incorporating Amendments 1, 2 and 3

Section 8.4). Subjects will receive up to 14 days of study drug (maximum 15 days in prespecified cases, see Section 10.2), administered intravenously 4 times per day.

15.1 Safety Variables

Safety variables will include the following:

- Adverse events.
- Serious adverse events, including deaths.
- Vital signs (body temperature, blood pressure, heart rate, respiratory rate, and SpO₂).
- MELD score.
- Encephalopathy score.
- Laboratory parameters other than SCr.

Adverse events will be collected from the start of study drug administration, during treatment and up to 7 days post end of treatment and at each evaluation. Adverse events considered serious will be collected up to 30 days after the end of treatment. Deaths up to 90 days will be reported as SAEs. Adverse events will be classified by Medical Dictionary for Drug Regulatory Activities (MedDRA) system organ class, preferred term, severity, and seriousness, as well as by the investigator's assessment of the relationship of the AE to the study drug.

15.2 Subject Accounting and Baseline Characteristics

A summary of the study completion status and reasons for discontinuation will be provided for each treatment group. Baseline characteristics (age, gender, race, etc) will be summarized. The number of subjects with medical conditions within each body system will be reported. Summaries of the extent of exposure and protocol deviations will also be provided.

15.3 Statistical Methodology

15.3.1 Sample Size Calculation

NOTE: Based on REVERSE, subjects without a known event of pre-enrollment LVP at least 4 L within 2 days of randomization and OT-0401 subjects with baseline SCr no more than 7 mg/dL. SCr values were included while the subjects were on treatment, up to 24 hours after the final dose of study drug. SCr values were excluded after RRT and transplant. If a subject died within 10 days after the reversal, then the subject did not have a reversal. If a subject has an RRT by the 30-day follow-up visit, then the subject did not have a reversal. Three REVERSE terlipressin subjects who achieved a reversal after the 24 hour window were counted as reversals because they would have continued on study drug based on the CONFIRM trial design through the reversal.

With a 2:1 randomization of terlipressin to placebo and an interim analysis after 50% of the subjects have completed Day 14 or Discharge, 300 subjects will provide 89.76% power to detect a statistically significant difference between the groups, 200 subjects in the terlipressin group and 100 subjects in the placebo group.

15.3.2 Interim Analysis

An interim analysis will be performed after 50% of the subjects have completed Day 14 or discharge, 150 subjects with approximately 100 in the terlipressin group and 50 in the placebo group. An O'Brien-Fleming spending function is used for the interim analysis alpha spending. For the interim analysis, the methods described in Section 15.3.6.1 will be followed.

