- Mortality up to 90 days after the first dose of study drug.

Statistical Methods:

Primary Efficacy Analysis:

[figure not shown]
• The primary efficacy variable of verified HRS reversal is defined as the percentage of subjects with 2 consecutive SCr values no more than 1.5 mg/dL at least 2 hours apart, while on treatment by Day 14 or discharge (on treatment defined as up to 24 hours after the final dose of study drug). Subjects must be alive without RRT for at least 10 days after achieving verified HRS reversal. SCr values collected after RRT, TIPS, liver transplant, or open-label vasopressor use will be excluded from the primary endpoint analysis. SCr values obtained after midodrine administration will be included if midodrine was started on Day 1, was administered for no more than 24 hours, and the subject was enrolled on or after 17 August 2018. SCr values will also be included if obtained after the administration of a single dose of dobutamine. Verified HRS reversal will be summarized by treatment group and analyzed using a Z score based on the upper alpha boundary values for the interim and final analyses. The upper alpha boundary value for the interim analysis is 2.79651. At the interim analysis, if the Z score is greater than 2.79651 then the study will stop

for early success. If the Z score is no more than 2.79651 then the study will continue to the final analysis. The final analysis will be successful if the Z score is greater than 1.97743.

Secondary Efficacy Analyses:

A Hochberg procedure for multiple testing and the alpha level corresponding to the Z score of the primary efficacy analysis will be used for testing the secondary efficacy analyses at either the interim analysis or the final analysis.

Sample Size:

Interim Analysis:

An interim analysis will be performed after 50% of the subjects have completed Day 14 or discharge, (150 subjects, with approximately 100 in the terlipressin group and 50 in the placebo group). An O'Brien-Fleming spending function is used for the interim analysis alpha spending.

3 Table of Contents, List of Tables, and List of Figures

Title page	1
Synopsis	23
Table of Contents, List of Tables, and List of Figures	28
ist of Tables	33
ist of Figures	33
List of Abbreviations	
Introduction	
1 Hepatorenal Syndrome	
2 Terlipressin	
3 Clinical Studies of Terlipressin in Subjects With HRS Type 1	

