^JA 12-lead ECG will be performed at baseline. Clinically relevant abnormalities found will be reported on the medical history page. The investigator may perform additional unscheduled examinations to manage or evaluate a suspected AE as clinically necessary.

^kBoth urine and blood samples for biomarker evaluation will be collected once at baseline; participation in this project will not affect participation in the main study.

Treatment should be continued until 24 hours after 2 consecutive SCr values no more than 1.5 mg/dL have been obtained, OR up to a maximum of 14 days (maximum of 15 days if SCr first reaches 1.5 mg/dL on Day 14, when the Day 14 assessments will be performed on Day 15). Window is (± 30 minutes).

mMust be performed at least once daily during active treatment AND until Day 14 (regardless of treatment status) or discharge, whichever occurs first. If SCr and/or BUN assessments are performed more than once daily as part of the subject's medical care, all values are to be recorded on the eCRF. At 30-day follow-up visit, collect SCr only (no BUN).

ⁿA blood sample for measurement of SCr must be drawn before discharge. The second verifying sample of SCr no more than 1.5 mg/dL must be taken at least 2 hours apart and must be consecutive.

^oIf a subject meets the primary end point (2 consecutive SCr values of no more than 1.5 mg/dL), the subject's survival and RRT status must be confirmed 10 days after the date of the second SCr. This follow up is required regardless of whether the subject remains hospitalized or has been discharged. If the subject has been discharged, follow-up may be by phone.

PRequired for evaluation of efficacy endpoints.

 $^{^{}q}$ Vital sign measurements include body temperature, respiratory rate, systolic and diastolic blood pressure, SpO₂ (pulse oximetric saturation), and heart rate. Time points for systolic and diastolic blood pressure and heart rate: predose and postdose at 5 (\pm 2) min and 2 (\pm 0.25) h for every dose. Time points for body temperature, respiratory rate, and pulse oximetric saturation (SpO₂): once daily.

^rConcomitant medications include IV solutions and blood products.

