13.2.3 Active Study Period (14 Days)

13.2.3.1 Dosing (Up to 14 Days)

The active study period extends from the initiation of study treatment through Day 14 (Day 15 as described in Section 10.4) or discharge from the hospital for any reason, whichever occurs first. Study drug will be administered as described in Section 10.3. Concomitant medications will be collected during this active study period.

See Table 13–1 for the schedule of assessments during the active study period.

13.2.3.2 End of Treatment, Discharge or Day 14

Treatment should be continued until 24 hours after 2 consecutive SCr values no more than 1.5 mg/dL have been obtained, OR up to a maximum of 14 days (maximum of 15 days if SCr first reaches 1.5 mg/dL on Day 14, when the Day 14 assessments will be performed on Day 15).

Following HRS reversal (SCr no more than 1.5 mg/dL), repeat values for SCr must be obtained a minimum of 2 hours after the first SCr value. Every effort must be made to collect these SCr values.

All information regarding paracentesis events, RRT, TIPS, liver transplant, or open-label vasopressor use must be collected.

The subject will be contacted to determine the status of survival without RRT at 10 days after the second SCr value no more than 1.5mg/dL is attained.

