15.3.6.1 Primary Efficacy Analysis

Incidence of verified HRS reversal is defined as the percentage of subjects with 2 consecutive SCr values no more than 1.5 mg/dL at least 2 hours apart, while on treatment by Day 14 or discharge (on treatment defined as up to 24 hours after the final dose of study drug). The subject must be alive without RRT for at least 10 days after achieving verified HRS reversal. SCr values after RRT, TIPS, liver transplant, or open-label vasopressor use will be excluded from primary end point analysis. SCr values obtained after midodrine administration will be included if midodrine was started on Day 1, was administered for no more than 24 hours, and the subject was enrolled on or after 17 August 2018. SCr values will also be included if obtained after the administration of a single dose of dobutamine.

Verified HRS reversal will be summarized by treatment group and analyzed using a Z Score based on the upper alpha boundary values for the interim and final analyses. The upper alpha boundary value for the interim analysis is 2.79651. At the interim analysis, if the Z score

is greater than 2.79651 then the study will stop for early success. If the Z score is no more than 2.79651 then the study will continue to the final analysis. The final analysis will be successful if the Z score is greater than 1.97743.

Table 15–2 shows the number of subjects with HRS Type 1 reversal that will be needed to achieve success at the interim analysis if the estimate of the placebo rate is accurate (approximately 12.5%).

Table 15–2: Potential Scenarios for Success at the Interim Analysis with a Placebo Rate of Approximately 12.5%

Endpoint	Terlipressin (N = 100) n (%)	Placebo (N = 50) n (%)	Z Score
Scenario 1	34 (34.0)	6 (12.0)	2.8723
Scenario 2	36 (36.0)	7 (14.0)	2.8098

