15.3.8 Missing Data

Unless otherwise stated, no imputation will be made for missing data.

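### Does the interim trigger at Day 14 or discharge let the trial be judged before the 10-day part of the primary endpoint is known?

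*Combined protocol and SAP*

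**What the plan says.** The trigger appears three times. Section 15.3.2 says: "An interim analysis will be performed after 50% of the subjects have completed Day 14 or discharge". Section 15.3.1 plans for "an interim analysis after 50% of the subjects have completed Day 14 or Discharge". The Synopsis gives the size as "150 subjects, with approximately 100 in the terlipressin group and 50 in the placebo group".

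Section 15.3.2 adds: "For the interim analysis, the methods described in Section 15.3.6.1 will be followed". That section defines the endpoint as two consecutive creatinine (SCr) values of at most 1.5 mg/dL, with the further condition: "The subject must be alive without RRT for at least 10 days after achieving verified HRS reversal". It also sets the interim boundary at Z above 2.79651 and the final boundary at Z above 1.97743.

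The 10-day status is a scheduled item. A footnote to Table 13-1 says that "survival and RRT status must be confirmed 10 days after the date of the second SCr", whether or not the subject has left hospital, and Section 13.2.3.2 repeats it: "The subject will be contacted to determine the status of survival without RRT at 10 days after the second SCr value". On missing values, Section 15.3.8 says: "Unless otherwise stated, no imputation will be made for missing data".

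**The concern.** The event that triggers the interim and the event that completes the endpoint differ. A non-responder is final at Day 14 or discharge. A responder is final only 10 days after the second qualifying SCr. Among recently completed subjects, open outcomes therefore occur only in responders.

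Crossing the boundary stops the trial. If data were cut on the trigger date, open reversals on terlipressin scored as not yet responders could hide a crossing that the completed data would show, and enrolment would go on toward 300. Open reversals on placebo scored the same way could stop the trial on a Z that the completed data do not support. Two of the four secondary endpoints tested after interim success also run to Day 30, later than the trigger.

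**Working it through.** **1. The plan's own figures.** The classical two-look O'Brien-Fleming boundary at 50% information, two-sided alpha 0.05, solves to 2.79651 and 1.97743, as stated. The pooled two-proportion statistic is

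Z = (x₁/100 − x₂/50) / √[p(1−p)(1/100 + 1/50)], with p = (x₁+x₂)/150.

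Table 15-2, Scenario 1 (34 v 6): Z = 2.8723, as stated. Scenario 2 (36 v 7): Z = 2.8088 against 2.8098 printed. The small difference does not affect the crossing.

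**2. How long an outcome stays open.** A second SCr on Day d is resolved on Day d + 10. A subject followed to Day 14 is resolved at completion only if d ≤ 4. A responder discharged when treatment ends, 24 hours after the second SCr (Section 10.4), has about 9 days open. The most is 10 days, when the second SCr falls on the completion day. If d were equally likely to be any day from 3 to 14 in subjects who stay 14 days (an assumption), the mean open time would be (0+0+1+2+…+10)/12 = 55/12 = 4.6 days. Windows of 5 and 10 days therefore give a fair range.

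**3. How many are open.** The documents give no accrual rate, so I take 5, 11 and 30 subjects a month as a range. The chance that one of the 150 is inside the window is

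o = (days open × monthly accrual / 30.4) / 150.

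At 10 days and 11 a month, o = (10 × 11 / 30.4)/150 = 0.0241. The placebo rate is 12.5% (Section 15.3.6.1). The planning rate for terlipressin is not visible, and 28.5% is assumed. Expected responders on completed data are 100 × 0.285 + 50 × 0.125 = 34.75, so about 34.75 × 0.0241 = 0.84 are open.

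**4. Worst case: cut on the trigger date, open reversals scored as not yet responders.** Exact enumeration over both binomials gives a 25.48% chance of crossing on completed data. Compared with that:

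| Days open | Subjects/month | o | True crossings missed | Stops not supported by completed data (of all trials) |
|---|---|---|---|---|
| 5 | 5 | 0.0055 | 2.5% | 0.35% |
| 5 | 11 | 0.0121 | 5.3% | 0.71% |
| 5 | 30 | 0.0329 | 12.8% | 1.53% |
| 10 | 5 | 0.0110 | 4.8% | 0.65% |
| 10 | 11 | 0.0241 | 9.9% | 1.24% |
| 10 | 30 | 0.0658 | 21.7% | 2.13% |

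In the unsupported stops at 10 days open, the mean completed Z is about 2.6.

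**5. Effect on inference.** With both arms at 12.5%, the interim crossing probability is 0.091% on completed data and 0.087% under this scoring (10 days, 11 a month). Simulation to 300 subjects gave power of 90.2% with either cut. One-sided rejection under the null was 2.16 to 2.18% with either cut, and 99.4% of missed crossings succeeded at the final analysis.

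**6. What the plan leads an analyst to do.** Section 15.3.2 fixes a time after which the look takes place and imports the 10-day condition. Table 13-1 and Section 13.2.3.2 require the status to be collected, and Section 15.3.8 rules out filling it in. Together these point to waiting for the pending contacts. The last falls about Day 24, or Day 25 under the Day 14/15 exception, so the wait is at most about 10 days. With that wait, every effect in step 4 disappears.

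**7. Day 30 secondaries.** A trigger-date cut with completion at Day 14 would leave 16 × accrual/30.4 = 2.6, 5.8 or 15.8 of the 150 short of Day 30. But Section 15.3.6.2 gives the alpha for these tests after interim success. It gives no date, and does not say that they use the interim cut.

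**The case for a change.** The best case for a change is that permission to wait is not a requirement. A team could cut at the trigger, score open reversals as not yet responders, and claim to follow the text. Table 13-1 gives the 10-day check its own column, apart from Day 14 or discharge, so the protocol itself treats them as separate events. One subject can also decide the matter: 33 v 6 gives Z = 2.764 where 34 v 6 gives 2.872. A rule that can stop a pivotal trial deserves a written data cut, and one sentence would supply it.

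It stands that no data-cut sentence is visible. The rest carries less weight. The one-subject reversal uses minimum winning counts, where one fewer success fails by construction. A separate column for the 10-day check shows that the data will be collected, which favours waiting. Silence in the public text is also weak evidence: the DSMB charter cited in Section 14 is not supplied, and sample-size text next to the interim paragraph in the Synopsis is not visible. Finally, every adverse figure needs a cut on the trigger date. A lag of 10 days for data cleaning alone would remove the effect on the primary endpoint.

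**Conclusion.** No change is needed. The missing detail is real, but following the plan as written fills it sensibly: the interim comes after the trigger, on an endpoint that includes the 10-day condition, using a status that sites must record.

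If the cut were nevertheless made on the trigger date, the central estimate is 5.3 to 9.9% of true interim crossings missed and 0.7 to 1.2% of trials stopping without support from completed data. This rests on 28.5% v 12.5%, 11 subjects a month, 5 to 10 days open and not-yet scoring. The upper figure of 21.7% needs both 30 subjects a month and a full 10 days open for every responder. The harm would be to the timing of the stop and the reported interim Z; type I error and overall power stay essentially the same. The Day 30 point depends on the same unstated cut and adds nothing separate.

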15.3.3 Subject Populations

The populations that will be utilized for this study are defined below.

15.3.3.1 Intention to Treat Population

The intention to treat (ITT) population is defined as all randomized subjects. Treatment classification will be based on the randomized treatment. The ITT population defined in this way complies with the ITT principle expressed in ICH E9. This will be the primary population for analysis of efficacy endpoints.

